8.3.2.3 Performance Outcomes and Quality of Life

The baseline evaluation for the quality of life outcomes will be the final evaluation prior to the OTL-101 infusion.

The number (%) of subjects choosing each answer to the questions “How have you been feeling in general?” and “Can the patient practice sports?” will be summarized at each visit. Changes from baseline to each subsequent visit will be summarized using the number (%) of subjects whose status improved/no change/deteriorated.

The number of days absent from school and the change from baseline will be summarized by visit.

Scores on the Lansky and Karnofsky performance scales and the change from baseline will be summarized by visit.

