1.1.1 Severe Combined Immunodeficiency due to Adenosine Deaminase Deficiency

Severe combined immunodeficiency (SCID) is a heterogeneous group of inherited disorders characterised by a profound reduction or absence of T lymphocyte function ([Chinn 2015](#)). Adenosine deaminase (ADA)-SCID was identified almost four decades ago and represents approximately 15-20% of all cases of SCID. Adenosine deaminase is a ubiquitous enzyme whose deficiency results in metabolic toxicity. The main features of the disease are impaired differentiation and function of T, B and natural killer (NK) lymphocytes, recurrent infections, and failure to thrive. In addition, non-immunological abnormalities occur as the consequence of the systemic metabolic defect, indicating that the disease is more complex than other forms of SCID. Adenosine deaminase-SCID is a genetic disorder and mutations in the *ADA* gene cause a lack or the poor functioning of the ADA enzyme leading to accumulation of Ado, d-Ado, and adenine deoxyribonucleotides (d-AXP) in plasma, red blood cells (RBC), and tissues. The severity of genetic mutations and the residual ADA activity are usually related to the age of onset, clinical manifestations, and levels of d-AXP ([Hirschhorn 1990](#)).

The majority of ADA-SCID patients are diagnosed in the first year of life. The patients rarely survive beyond 1 to 2 years unless immune function is restored, or contact with pathogens is avoided by creating a sterile environment around the patient (the so-called “bubble-children”). Lymphopenia, absence of both cellular and humoral functions, developmental delay, failure to thrive, and recurrent infections due to fungal, viral, and opportunistic agents are the key features of these early onset forms. These forms are essentially indistinguishable from other forms of SCID, with the exception for bony abnormalities in 50% of patients.

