1. Provision of written informed consent prior to any study related procedures. In this study consent must be provided by the parents/legal guardians and, where applicable according to local laws, a signed assent from the child,
2. Subjects ≥ 30 days and < 18 years of age,
3. With a diagnosis of ADA-SCID based on:

Evidence of ADA deficiency, defined as:

- i. Decreased ADA enzymatic activity in erythrocytes, leukocytes, skin fibroblasts, or in cultured fetal cells to levels consistent with ADA-SCID as determined by the reference laboratory, or
- ii. Identified mutations in ADA alleles consistent with a severe reduction in ADA activity,

Evidence of ADA-SCID based on either:

- i. Family history of a first order relative with ADA deficiency and clinical and laboratory evidence of severe immunologic deficiency, or
- ii. Evidence of severe immunologic deficiency in subjects prior to the institution of immune restorative therapy, based on
 - Lymphopenia (absolute lymphocyte count (ALC) < 400 cells/ μ L) OR absence or low number of T-cells (absolute CD3+ count < 300 cells/ μ L), or
 - Severely decreased T lymphocyte blastogenic responses to phytohemagglutinin (either $< 10\%$ of lower limit of normal controls for the diagnostic laboratory, or $< 10\%$ of the response of the normal control of the day, or stimulation index < 10), or
 - Identification of SCID by neonatal screening revealing low TREC levels.
4. Ineligible for matched family allogeneic BM transplantation, defined as the absence of a medically eligible HLA-identical sibling or family donor, with normal immune function, who could serve as an allogeneic bone marrow donor.
5. Females of child-bearing age will be required to provide a negative pregnancy test 30 days prior to Visit 2.
6. Subjects and their parents/legal guardians must be willing and able to comply with study restrictions and to remain at the clinic for the required duration during the study period and willing to return to the clinic for the follow up evaluation as specified in the protocol.

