9.4 Sample Size Considerations

Due to the ultra-orphan nature of this indication, the sample size for this study is based on practical considerations. Specifically, the number of ADA-SCID patients expected to meet eligibility criteria yearly is around four to five. With a planned enrollment of three to six subjects per year, the sample size (N=10) for this study is considered reasonable.

It should be noted that the sample size will provide precision of 15% for 100% success (survival) at any particular time point. Precision is here defined as the half-width of the two-sided 95% CI using the Exact Binomial computations.

Ten subjects receiving OTL-101 will participate in this study.

Although all subjects will be evaluable for the first analysis at 6 months post OTL-101 infusion, the first five subjects will be reviewed to monitor the outcome of the study treatment. Sample size considerations for the first analysis of five subjects completing the 6-month follow-up assessment is based on realistic enrollment for this orphan indication. Experts in the field of HSCT and gene therapy use RBC ADA enzyme activity >0 U, absolute CD3+ T-cell counts $\geq 200/\text{mm}^3$, and peripheral blood samples positive for vector sequences by qPCR ($>1/10,000$ cells) as predictors of survival and event free survival and ultimately the success of the OTL-101 treatment. These parameters achieve plateau between 3 and 4 months post-intervention, therefore, a 6-month data cut for this interim analysis should be indicative of the final study outcomes.

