8.3.2.6 Immune Reconstitution

Immune reconstitution will be assessed using lymphocyte subsets. Absolute numbers and percentage of $CD3^+$, $CD4^+$, $CD8^+$ and $CD4^+/CD45RO^+$ T-lymphocytes, $CD19^+$ B-lymphocytes and $CD56^+/CD16^+$ NK cells will be measured.

For each of the lymphocyte subsets, the actual value and change from baseline will be summarized at each visit. The median value and range will be plotted over time on a logarithmic scale and individual counts will be plotted along with the age-dependent normal ranges provided by the study site.

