8.4.7 Vital Signs, Height and Weight

Vital signs (temperature, pulse rate, respiratory rate, systolic and diastolic blood pressure and oxygen saturation), height and weight are measured over time.

The baseline evaluation for each of the vital signs, height and weight will be the final evaluation prior to the OTL-101 infusion.

For each parameter, the actual value and change from baseline will be summarized at each visit using descriptive statistics.

Any vital signs found to be out of range will be categorized as not clinically significant or clinically significant. For each vital sign, the number (%) of subjects with clinically significant evaluations will be summarized by visit and at any time post-infusion.

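### Height and weight are tabulated only as raw values and raw change, and the sports and school items have no rule for children too young for them, so growth and ageing alone can move these summaries

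*SAP*

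**What the plan says.** **Height and weight.** SAP 8.4.7, under Safety Evaluations, takes the last value before infusion as baseline and then says: "For each parameter, the actual value and change from baseline will be summarized at each visit using descriptive statistics". It mentions no percentile, z-score or other age reference.

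**Sports, general feeling and school.** SAP 8.3.2.3 tabulates the answers on general feeling and on ability to practise sports at each visit. It then says: "Changes from baseline to each subsequent visit will be summarized using the number (%) of subjects whose status improved/no change/deteriorated". School days missed and Lansky/Karnofsky scores get a value and a change from baseline. The section gives no age condition, no category for a child to whom an item does not apply, and no denominator rule.

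**Lymphocyte subsets.** SAP 8.3.2.6 says: "For each of the lymphocyte subsets, the actual value and change from baseline will be summarized at each visit". It also plots each child's counts against the site's age-dependent normal ranges. SAP 8.3.2.2 does the same for immunoglobulins.

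**Who is studied.** Protocol 4.1 admits "Subjects ≥ 30 days and < 18 years of age". Protocol 3.1 describes a single cohort and Protocol 3.5 gives two years of follow-up. Protocol 1.1.1 lists failure to thrive among the main features of the disease. WHO growth z-scores appear only in the adverse event grading table in Protocol Appendix 4.

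**The concern.** With no concurrent control, a change from baseline has to be read on its own terms. For a growing child, a gain in kilograms or centimetres is the expected result whatever the treatment does. A table of raw gains therefore cannot separate a child who thrives from one who falls steadily behind.

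The sports and school items raise a related problem. An infant cannot practise sports and does not attend school. If that is recorded as an ordinary answer, growing older changes it. If it is left blank, there is no baseline, and the SAP does not say what happens to the change.

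Comparison with the other cohort is also at stake. SAP section 6 says that at the first analysis, with at least five subjects at Month 6, secondary and exploratory endpoints will be compared with the fresh-formulation study. Quality of life is one of those endpoints. A different age mix in the two cohorts could then look like a difference between formulations.

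**Working it through.** **Inputs**
- Cohort size: Protocol 9.4, "Ten subjects receiving OTL-101 will participate in this study".
- Age range and follow-up: Protocol 4.1 and 3.5.
- Minimum at the first analysis: 5 subjects, SAP section 6.
- Not given in either document: ages at infusion, the answer options and coding of the sports and school items, and growth reference values.

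**The plan's own figure.** Protocol 9.4 states: "It should be noted that the sample size will provide precision of 15% for 100% success (survival) at any particular time point". The exact two-sided lower limit for 10/10 is 0.025^(1/10) = 0.6915, so the half-width is (1 − 0.6915)/2 = 0.154. The 15% reproduces. It concerns survival and does not bear on this point.

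**Step 1: how much of follow-up is growth.** Age at Month 24 is baseline age plus 24 months.

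| Age at infusion (months) | Age at Month 24 (months) | Ratio |
|---|---|---|
| 1 | 25 | 25.0 |
| 12 | 36 | 3.0 |
| 60 | 84 | 1.4 |
| 120 | 144 | 1.2 |

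**Step 2: height and weight.** Write the reference at age a, simplified, as mean M(a) and standard deviation S(a). A child at z-score z measures Y(a) = M(a) + z·S(a). Over 24 months, with z going from z0 to z1:

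raw change = [M(a+24) − M(a)] + [z1·S(a+24) − z0·S(a)]

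The first bracket is normal growth and is positive in any child still growing. Raw change stays positive until the second bracket is negative enough to cancel all of it. Faltering is z1 − z0 < 0, and this can occur while raw change is well above zero. Because a differs between children, z1 − z0 cannot be recovered from a group mean in kg or cm. Measured values by visit have the same limitation. No number is put on this, because the documents hold no growth reference values.

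**Step 3: sports.** Suppose k of n children are coded unable at baseline only because of age, and able later. With no treatment effect they add k/n to the improved count. One child adds 1/10 = 10 percentage points in the full cohort and 1/5 = 20 points at a first analysis of five. The documents do not give k. It is 0 if the form skips the question for infants; as an assumption only, k = 3 of 10 would give 30%.

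**Step 4: school.** Suppose k of 10 children are recorded with 0 days at baseline because they are not at school, and later miss d days each. The mean change is k·d/10. As an assumption, k = 3 with d = 2, 5 or 10 gives +0.6, +1.5 or +3.0 days. That reads as worsening, the opposite direction from sports. It needs children who reach school age during follow-up; a 12-month-old ends the study at 36 months.

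**Step 5: the SAP against itself.** For immunoglobulins and lymphocytes the SAP brings in an age reference, on individual plots. For height and weight it brings in none.

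**The case against.** **Growth problems can surface as adverse events.** Appendix 4 grades a weight-for-length z-score below −3 as Grade 3, and SAP 8.4.1.2 counts events of Grade 3 or higher. This stands in part. It depends on the investigator reporting the event, the table has no entry for slow height growth, and Protocol 9.3.4 names a different grading system (CTCAE). It also does not make the height and weight tables interpretable.

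**The questions are adapted to age.** Protocol 7.2 says so, and the case report form, which may hold a not-applicable answer, is not available here. SAP 8.3.2.3 tabulates every answer, so such a category would be visible. This stands, and it is why the size of the sports and school effect is unknown. It does not supply the missing rule for computing change.

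**The summaries are descriptive.** Protocol 9.3.2 says so and no decision depends on them. True, but SAP section 6 still plans a comparison with the fresh-formulation study, and a descriptive table should describe the right quantity.

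**Stronger readings that the documents do not support**
- A reader might infer that growing older is scored as improvement on all these measures. Only general feeling and sports get an improved or deteriorated label. Height, weight, school days and cell counts get a raw change, and school absence would tend the other way.
- A reader might take Protocol 1.1.1, "The majority of ADA-SCID patients are diagnosed in the first year of life", and conclude that at least half of the cohort will count as improved on sports by age alone. That sentence concerns diagnosis in patients generally, not age at infusion here. The conclusion also needs assumed coding at both visits.
- A reader might think that cell counts have no age reference. The individual plots carry one, and with 10 subjects that covers every child. The documents do not say which way age moves the counts.
- A reader might treat growth as an efficacy outcome. It is summarised under safety, and neither document names it as an endpoint.

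**Conclusion.** The point holds in two parts.

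1. **Height and weight (SAP 8.4.7).** Raw value and raw change cannot show growth faltering in growing children followed for 24 months, in a disease for which the protocol names failure to thrive. This rests only on the eligible age range and on normal growth.
2. **Sports and school (SAP 8.3.2.3).** The SAP does not say how a child too young for the item is coded or counted, so age alone could change that child's category or absence count. Per child the effect is 10 percentage points in a full cohort of 10. The number of children affected cannot be stated from the documents and may be zero.

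The lymphocyte table is a lesser matter, where an age-referenced row would help but is not essential. No primary endpoint and no sample-size figure changes. The revision is worth making before the tables are programmed, because a clearly better summary can be built from data already collected.

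**What to change.** - **SAP 8.4.7:** report height, weight and weight-for-length or BMI as age- and sex-standardised z-scores by visit, with change in z, using age on the measurement date. Use the WHO references cited in Appendix 4 where they cover the age. Its underweight entries use weight-for-length under 2 years, weight-for-height from 2 to 5, and BMI above 5 to 19. The SAP should therefore name its references for height and weight for age, and say what is done outside the covered ages: a subject just under 18 at infusion is just under 20 at Month 24. SAP Table 1 shows height before infusion at screening only, so baseline weight-for-length or BMI should use the screening pair.
- **SAP 8.3.2.3:** limit the sports and school change summaries to subjects for whom the item applies at both baseline and the visit. Show not applicable for age as its own category, outside the improved and deteriorated counts, and state the denominator. Fix in advance how applicability is decided.
- **SAP 8.3.2.6 (optional):** add the number and percentage within the site's age-dependent normal range at each visit. Those ranges are already held for the plots.

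**Cost.** Date of birth, sex, height and weight are already collected, so the growth and cell-count changes are programming only. The not-applicable category is also programming if it is derived from a stated age rule or an existing form answer; otherwise it needs a small form change. The real downside is smaller denominators for the sports and school items in a study of 10.

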8.3.2.4 Rate of Severe Infections

Infections will be recorded as adverse events. The infections of interest in this study are severe infections or opportunistic infectious episodes, defined as infections requiring hospitalization or prolonging hospitalization and/or documented infections by opportunistic pathogens (e.g. interstitial pneumonia, intractable diarrhoea).

The number (%) of subjects reporting severe infections or opportunistic infectious episodes along with the number of events reported will be summarized. In addition, the infection rate will be calculated as the number of infections/the total follow-up time. The rate will be calculated both for the entire group and for each individual subject. The subject infection rate will be summarized using descriptive statistics. In addition to the rate for the entire follow-up period, the rate will be calculated for both the first 12 months following transplant and for the remaining study period.

8.3.2.5 Response to Tetanus Vaccination

Tetanus antibodies will be measured in subjects who have stopped immunoglobulin replacement and have received a tetanus vaccination.

Pre-vaccination and post-vaccination titres will be summarized by vaccination number.

Subjects will be considered to have mounted a protective antibody response to tetanus if they have a titre of anti-tetanus antibodies >0.15 IU/ml. The number (%) of subjects who mounted a protective antibody response to tetanus will be summarized.

8.3.2.6 Immune Reconstitution

Immune reconstitution will be assessed using lymphocyte subsets. Absolute numbers and percentage of $CD3^+$, $CD4^+$, $CD8^+$ and $CD4^+/CD45RO^+$ T-lymphocytes, $CD19^+$ B-lymphocytes and $CD56^+/CD16^+$ NK cells will be measured.

For each of the lymphocyte subsets, the actual value and change from baseline will be summarized at each visit. The median value and range will be plotted over time on a logarithmic scale and individual counts will be plotted along with the age-dependent normal ranges provided by the study site.

8.3.3 Exploratory Efficacy Endpoints

8.3.3.1 Use of PEG-ADA Enzyme Replacement Therapy

The time to withdrawal of PEG-ADA ERT will be calculated (in months), using the stop date on the concomitant medication form, as:

$$12^*(\text{stop of PEG-ADA ERT} - \text{date of infusion})/365.25.$$

Time to withdrawal of PEG-ADA ERT will be summarized using descriptive statistics and, if appropriate, estimated from a Kaplan-Meier curve in which subjects who are still receiving PEG-ADA ERT will be censored at the time of their last visit.

8.3.3.2 T Cell Receptor Excision Circles (TREC)

TREC levels will be summarized at each visit using descriptive statistics. Plots of the median and range over time on a logarithmic scale will be produced. In addition, individual subject plots of TREC levels over time will be produced.

8.3.3.3 T Cell Receptor V β Panel Results

TCR V- β usage, categorized as normal/abnormal, will be summarized by visit and overall using the number (%) with an abnormal evaluation at any post-infusion visit.

8.3.3.4 T Lymphocyte Response to Phytohemagglutinin (PHA)

T lymphocyte response to PHA, categorized as normal/abnormal, will be summarized by visit and overall using the number (%) with an abnormal evaluation at any visit.

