5.1.3 Baseline (Visit 3)

Pre-Conditioning (Assessment C)

After BM harvest and if the autologous OTL-101 product has met the release criteria ([Section 3.7.1](#)), additional baseline samples must be collected for the following tests within 1 week before the first administration of Busulfan:

- Physical examination, including vital signs (temperature, pulse rate, respiratory rate and blood pressure). Temperature can be measured as per standard clinic practice,

- Hematology (see [Table 3](#)),
- Prothrombin or INR and PTT,
- Biochemistry (see [Table 3](#)),
- Serum HCG (pregnancy test) if female of child-bearing age (and if more than 28 days have elapsed since the screening test),
- Urinalysis,
- Pulse oximetry,
- Interval history (including routine review of systems, including infectious symptoms (e.g., fever), AEs and concomitant medications),
- Measurement of immune function:
 - Absolute numbers of CD3+, CD4+ and CD8+ T-lymphocytes, CD19+ B-lymphocytes and CD56+/CD16+ (or CD56+/CD3-) NK cells, CD4+/CD45RA+ (naïve) and CD4+/CD45RO+ (memory) T cells,
 - TREC levels,
 - TCR V β usage,
 - lymphocyte response to phytohemagglutinin (PHA) (if sufficient cells),
 - Serum immunoglobulin (IgG, IgA, IgM).

Please note: the above immune function tests can be performed at any point after provision of consent/assent and prior to Busulfan administration in younger subjects if deemed appropriate by the Investigator.

- Peripheral blood mononuclear cells (PBMC) and serum banking for RCL determination. These tests can be performed at any time following BM harvest (Visit 2: Assessment B) and prior to OTL-101 administration (Visit 3: Assessment F) in younger subjects if deemed appropriate by the Investigator.
- Measurements of erythrocyte ADA enzymatic activity and erythrocyte deoxyadenine nucleotide levels. These tests can be performed at any time following BM harvest (Visit 2: Assessment B) and prior to OTL-101 administration (Visit 3: Assessment F) in younger subjects if deemed appropriate by the Investigator.

The Investigator must ensure a PICC line or central venous catheter is in place prior to the start of Busulfan conditioning.

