| 1. Subjects will be admitted to the hospital for Visits 2 and 3. 2. During the infusion of OTL-101 vital signs will be monitored according to standard institute protocols. 3. Biochemistry samples will include the assessment of parameters listed in Table 3. Albumin ALT, AST, ALP will be measured at all time points indicated in this table. Total bilirubin, total protein, creatinine, blood urea, sodium, potassium, chloride, and calcium will be measured at screening, baseline, Day 1 and all follow-up visits (Month 1 to Month 24). Magnesium and phosphate will be measured only at pre-harvest and baseline time points. 4. Hematology samples will include the assessment of parameters listed in Table 3 and will be measured at all time points indicated in this table. 5. If cytogenetic testing was not performed on cells from amniocentesis, assessment should be by karyotype, CGH, and WES 6. Serum pregnancy tests are required in females of child-bearing potential at screening, prior to bone marrow harvest, prior to conditioning (Busulfan) treatment, and before the infusion of OTL-101. Any positive test will immediately result in the withdrawal of the subject from the study and should be reported as per guidance in Section Error! Reference source not found. 7. Urinalysis will include the assessment of parameters listed in Table 3 and will be measured at all time points indicated in this table. Any abnormalities detected on dipstick at Screening, Pre-harvest and Baseline will require repeat dipstick and microscopic examinations. 8. If there is any evidence of severe lung disease on the screening chest X-ray, a CT scan is required in order to establish if the subject meets any of the specified pulmonary exclusion criteria defined in Section Error! Reference source not found. 9. Standard post-transplant medication will be administered from Day 0 and recorded in the eCRF. 10. Immune function will be assessed absolute numbers of CD3+, CD4+ and CD8+ T-lymphocytes, CD19+ B-lymphocytes and CD56+/CD16+ (or CD56+/CD3-) NK cells, CD4+/CD45RA+ (naïve) and CD4+/CD45RO+ (memory) T cells, TREC levels, TCR Vβ usage, lymphocyte response to PHA (if sufficient cells), and serum immunoglobulin (IgG, IgA, IgM). 11. The immune function tests required for Visit 3, Assessment C can be performed at any point after provision of consent/assent and prior to Busulfan administration in younger subjects if deemed appropriate by the Investigator. 12. These test can be performed at anytime following BM harvest (Visit 2: Assessment B) and prior to OTL-101 administration (Visit 3: Assessment F) in younger subjects if deemed appropriate by the Investigator. | | | | | | | | | | | | | | |

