| Visit window | +/- 1 week | +/- 1 week | +/- 2 weeks | +/- 2 weeks | +/- 2 weeks | +/- 4 weeks | +/- 4 weeks | +/- 4 weeks | |
| Physical examination | X | | X | X | X | X | X | X | X |
| Vital Signs | X | | X | X | X | X | X | X | X |
| Weight (kg) | X | | X | X | X | X | X | X | X |
| Height (cm) | X | | X | X | X | X | X | X | X |
| Biochemistry sample ² | X | X | X | X | X | X | X | X | X |
| Hematology sample ³ | X | X | X | X | X | X | X | X | X |
| Questionnaire/QoL scale | | | | X | | X | X | X | X |
| Infectious episodes | X | | X | X | X | X | X | X | X |
| Adverse events | X | X | X | X | X | X | X | X | X |
| Concomitant Medication ⁴ | X | X | X | X | X | X | X | X | X |
| Record IgG and PEG-ADA therapy received | X | X | X | X | X | X | X | X | X |
| Immune function ^{5,6} | X | | X | X | X | X | X | X | X |
| Serum banking for RCL | | | X | X | | X | | X | X |
| Vector integration analysis | | | X | X | | X | X | | |
| Leukaemia assessment ⁷ | | | | X | | X | X | X | X |
| T-cell proliferation to PHA | | | | X | X | X | X | X | X |
| Antibodies to tetanus toxoid | | | | | | X | X | X | X |
| Presence of ADA gene in PBMC/granulocytes and/or lineage-sorted cells | | | X | X | | X | | X | X |
| RCL assay in PBMC | | | X | X | | X | | X | X |
| ADA enzymatic assay | X | | X | X | X | X | X | X | X |
| Deoxyadenine nucleotides in RBC | X | | X | X | X | X | X | X | X |
| Responder assessment ⁸ | | | | X | | | | | |

1. Day 42 assessment will use laboratory parameters to confirm if hematologic reconstitution has occurred. If this has not happened by Day 42 rescue medication, as per standard institute procedure, will be implemented. Any treatment administered to the subject will be recorded in the eCRF.
 2. Biochemistry samples will include the assessment of parameters listed in Table 3. Albumin ALT, AST, ALP will be measured at all time points indicated in this table. Total bilirubin, total protein, total protein, creatinine, blood urea, sodium, potassium, chloride, and calcium will be measured at screening, baseline, Day 1 and all follow-up visits (Month 1 to Month 24). Magnesium and phosphate will be measured only at baseline and the conditioning time points.
 3. Hematology samples will include the assessment of parameters listed in Table 3 and will be measured at all time points indicated in this table.
 4. Standard post-transplant medication will be administered from Day 0 and recorded in the eCRF.

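### The overall PHA summary in SAP 8.3.3.4 includes the pre-treatment baseline, so it cannot fall below the proportion abnormal at baseline, whatever the treatment does

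*SAP*

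**What the plan says.** SAP 8.3.3.4 has PHA response, classified as normal or abnormal, "summarized by visit and overall using the number (%) with an abnormal evaluation at any visit". The section directly before it, SAP 8.3.3.3, has TCR V-beta usage "summarized by visit and overall using the number (%) with an abnormal evaluation at any post-infusion visit". The two rules differ only in the post-infusion restriction.

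PHA is tested before treatment. Protocol 5.1.3 lists it among the immune function tests at Visit 3, Assessment C: "lymphocyte response to phytohemagglutinin (PHA) (if sufficient cells". In the SAP's Table 1, footnote 10 includes PHA in the baseline immune function panel. Footnote 11 adds, for younger subjects, that "The immune function tests required for Visit 3, Assessment C can be performed at any point after provision of consent/assent and prior to Busulfan administration".

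After infusion, the SAP's Table 2 has a separate row, "T-cell proliferation to PHA", marked at Months 6, 9, 12, 18 and 24 and at early termination. Footnote 5 of that table also places PHA under immune function, which is marked at Months 1 and 3 as well. The visit lists in Protocol 5.1.7 do not include PHA at Months 1 and 3.

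SAP section 6 says that at the first analysis the exploratory endpoints will be described and also compared with the data from the fresh-formulation study.

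**The concern.** PHA response is there to show whether T-cell function recovers. An overall count that includes the baseline sample mixes disease before treatment with results after it. A subject who is abnormal at baseline and normal at every later visit is still counted as abnormal overall.

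Two uses of the figure are affected. Within this study, a reader may take the overall percentage as a result of treatment when part or all of it is pre-treatment status. In the first-analysis comparison, if the same rule is applied to both cohorts, a difference in baseline PHA status would appear as a difference between formulations. Baseline has most weight at that analysis: for a subject with six months of follow-up, the Protocol 5.1.7 visit lists give a single post-infusion PHA result, at Month 6, so baseline is one of two.

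**Working it through.** The documents state no PHA abnormality rate, so there is no figure of the plan to reproduce. The check is on what the counting rule can return.

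**Inputs**
- n = 10 treated subjects (Protocol 9.4).
- b = proportion abnormal at baseline. Not in the documents; assumed from 30% to 100%.
- q = proportion abnormal at one or more post-infusion visits. Not in the documents; assumed 0%, 20% or 50%.

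For simplicity every subject is taken to have a baseline result.

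**Step 1: bounds.** The any-visit proportion U counts subjects abnormal at baseline, after infusion, or both. Hence max(b, q) ≤ U ≤ min(1, b + q). The lower bound needs no assumption about how the two are related: U is never below b.

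**Step 2: best case after treatment.** With q = 0, U = b exactly. For n = 10 that is 3/10 at b = 30%, 7/10 at b = 70% and 10/10 at b = 100%. A post-infusion count gives 0/10 each time.

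**Step 3: some abnormal results after treatment.** If baseline and post-infusion status were independent, U = 1 − (1 − b)(1 − q). For example, b = 30% and q = 20% give 1 − 0.70 × 0.80 = 44%.

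| Assumed b | U, q = 0 | U, q = 20% | U, q = 50% |
|---|---|---|---|
| 30% | 30% | 44% | 65% |
| 50% | 50% | 60% | 75% |
| 70% | 70% | 76% | 85% |
| 90% | 90% | 92% | 95% |
| 100% | 100% | 100% | 100% |
| Post-infusion rule, any b | 0% | 20% | 50% |

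Independence is a convenience. If the same subjects tend to be abnormal before and after, U moves down towards max(b, q), but not below it.

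**Step 4: how often the count is close to 10/10.** With q = 20% and independence, the binomial chance of at least 9 of 10 abnormal is 0.004 at b = 30%, 0.046 at 50%, 0.267 at 70%, 0.812 at 90% and 1.0 at 100%.

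**Step 5: comparison of cohorts.** Suppose no subject in either study is abnormal after infusion, and baseline rates are 30% in one and 70% in the other. The overall figures are 30% and 70%, a difference of 70 − 30 = 40 percentage points that comes entirely from baseline.

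**Step 6: what a post-infusion rule leaves open.** A count of any abnormal result grows with the number of tests. With an assumed 10% chance per visit, independent across five visits, it reaches 1 − 0.90^5 = 41%.

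**Step 7: other any-time summaries in the SAP.** Infectious episodes (8.4.3), leukaemia assessment (8.4.5), haematology (8.4.6.1), biochemistry (8.4.6.2) and vital signs (8.4.7) all limit the any-time count to the period after infusion. RCL testing (8.4.4) does not state the limit. No reason is given for treating PHA differently.

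**The case against.** It can be said that the separate PHA row appears only in the follow-up schedule, so the visits meant are the follow-up visits. That may be the intention, but the baseline panel includes PHA, and the neighbouring section shows that the authors write the restriction when they want it. The text should not rest on a guess.

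The stronger defence is that little depends on this line. PHA is exploratory, all efficacy summaries are descriptive (Protocol 9.6.4), and PHA does not enter the responder definition, survival, event-free survival or the stopping rules. The same sentence of the SAP calls for a by-visit summary, in which recovery would be visible. All of this stands and limits the harm. It does not correct the overall figure, which the SAP still commits to report.

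A reader might go further and infer that the figure will be near 100% abnormal whatever the treatment does, because a low PHA response is an entry criterion. The documents do not support that:
- In Protocol 4.1, "Severely decreased T lymphocyte blastogenic responses to phytohemagglutinin" is one of several alternatives, beside lymphopenia or low CD3 count and low TREC on neonatal screening. There is also a family-history route.
- The laboratory criteria are introduced as "Evidence of severe immunologic deficiency in subjects prior to the institution of immune restorative therapy, based on", which is not the study baseline. Protocol 6.2.1.1 has all subjects on PEG-ADA before infusion. Protocol 1.1.2.1 describes immune recovery on enzyme replacement as often incomplete, but gives no PHA rate.
- Baseline PHA depends on having enough cells, so some subjects may have no baseline result to count.

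It is also fair to say that limiting the count to post-infusion visits does not turn it into a measure of recovery, as step 6 shows.

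**Conclusion.** The point holds as a defect of definition with limited consequences. Read literally, the overall PHA proportion is bounded below by the proportion abnormal at baseline, and that bound does not depend on treatment or on any assumption about correlation. Its size depends on a baseline rate that the documents do not give: with no abnormal result after infusion, the overstatement is 3 of 10 subjects at an assumed 30%, 7 of 10 at 70% and 10 of 10 at 100%. A figure near 100% regardless of treatment follows only if the baseline rate is itself near 100%, which is not established. Nor can it be said that the figure would be taken for treatment failure. It could mislead a reader who sees it without the by-visit table, or who sees it set against the fresh-formulation study.

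**What to change.** In SAP 8.3.3.4, end the sentence as 8.3.3.3 does: "overall using the number (%) with an abnormal evaluation at any post-infusion visit". Leave the baseline result to the by-visit summary, where it is already reported, and apply the same rule to the fresh-formulation data at the first analysis. Optionally, add the number (%) of subjects with a normal PHA response at the last available visit, which speaks more directly to recovery than any cumulative count of abnormal results.

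The cost is a few words in the SAP. No new data, visits or protocol amendment are needed, and the optional line uses results already collected.
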